Background: Obesity is increasingly common in childhood and adolescence and is associated with high rates of abnormal cholesterol and high blood pressure, type 2 diabetes and cardiovascular disease. Studies suggest that regular physical activity can reduce cardiovascular risk factors in children. Despite evidence of its benefits, exercise training prescribed by physicians for overweight children is traditionally vague, developmentally inappropriate, and/or fraught with psychological barriers. There has been recent increased interest in the use of interactive new technologies to promote physical activity, prevent or reverse unhealthy weight and improve physical fitness in youth. **Objective:** To determine whether exercise counseling with BodyMedia, an online interactive accelerometer, has an effect on physical activity levels, fitness levels, and cardiometabolic measurements in pediatric patients with cardiovascular risk factors. **Design:** A randomized controlled pilot study of children at increased risk for atherosclerosis comparing exercise prescription combined with BodyMedia to a control group receiving physician counseling alone (standard of care). **Measures:** All study patients will be assessed at baseline and at the end of the study period directly for energy expenditure and physical activity using accelerometry; physical fitness will be assessed by standard VO₂ stress at the same time periods. Available blood pressure and lipid levels will be gathered from clinical encounters, and self-efficacy will be evaluated by questionnaires. **Primary Hypothesis:** This interactive technology coupled with support from exercise specialists will increase the energy expenditure of our patients over standard of care provider counseling. **Secondary hypotheses:** There will be greater improvement in measured physical fitness, lipid profiles, blood pressure, arterial stiffness, BMI, BMI percentile, and self-efficacy in the intervention group compared to control.

1. Specific Aims /Objectives

Primary aim: This pilot study seeks to compare the change in energy expenditure and fitness levels of patients seen in the Children's Hospital Preventive Cardiology program receiving standard of care provider exercise counseling to similar patients receiving FITT (Frequency, Intensity, Time, Type) exercise prescription and counseling combined with BodyMedia supported by an online interactive tool.

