Forty patients with hyperlipidemia, overweight/obesity and/or HTN received FITT counseling in addition to standard care counseling by physicians during their visit in the Preventive Cardiology Clinic. Subjects were divided into "compliant" and "non-compliant" groups on the basis of information gleaned from their follow up clinic visit notes. Those that were compliant showed improvement in their lipid profile, BMI and physical activity levels. In contrast, non-compliant patients either showed no change or worsened cardiovascular risk factors. We concluded that when children with cardiovascular risk factors adhere to an exercise prescription, improvements are often achieved, and successful weight loss is sometimes realized. Unfortunately, poor compliance with exercise prescriptions was again common, and limited the effectiveness of this therapeutic intervention.

4. Design and Methods

a. Study Design

A randomized controlled pilot study comparing exercise prescription based on the FITT principle combined with BodyMedia, an online supported accelerometer, to a control group receiving physician counseling alone (standard of care). All participants will wear an accelerometer to measure physical activity for one week at the start of the intervention. At the end of that week, patients who have worn the accelerometer for more than 8 hours per day for at least 3 days will be randomly assigned to either FITT

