counseling by a pediatric exercise physiologist + interactive accelerometer, or office provider counseling (standard of care). The intervention group will be asked to continue to wear the accelerometer everyday (most waking hours) and log their activity by regularly (3 times a week) uploading the device for a period of 3 months, use of the internet must be supervised by a parent or guardian. Their activity will be monitored via the online site on a regular basis by study personnel and feedback will be provided at least once a week through email and/or phone calls. At the end of the intervention all participants will be asked to again wear the accelerometer for 1 week to assess physical activity, and complete questionnaires assessing attitudes towards and self-efficacy around physical activity. Lipid levels and blood pressures, when obtained for clinical visits in Preventive Cardiology Clinic, will be evaluated for change over the course of the intervention. Participants will be given a non-invasive pulse wave velocity test. Pulse wave velocity testing is a painless non-invasive test to evaluate the time it takes for blood to move from the heart to the rest of the body. In practice, this involves using a fingertip probe placed lightly on the brachial artery – the internal aspect of the elbow, the carotid artery – side of the neck, and the femoral artery – groin area. This final measurement is easily performed through light clothing. In order to coordinate the timing of the pulse wave, four EKG electrodes are placed on the patient. The entire procedure takes about 15 minutes in experienced hands. There is no risk involved in this non-invasive procedure. It is less painful than a blood pressure measurement. The research study will require 2 visits to the Preventive Cardiology Clinic in Boston or Waltham, based on their preference. Each visit may take up to 1-1.5 hours.

b. Patient Selection and Inclusion/Exclusion Criteria

A sample of 60 patients at increased risk for atherosclerosis will be recruited from Preventive Cardiology.

Inclusion criteria:

Subjects will be eligible for enrollment based on the following criteria:

- 1) Patients at increased risk of atherosclerosis based on lipid profiles (TC > 199 mg/dL, HDL < 40 mg/dL, LDL > 129 mg/dL, blood pressure (SBP or DBP > 90th percentile), obesity (>85%BMI)
- 2) Ages 13-21 years
- 3) Reporting an average of less than 60 minutes per day of moderate to vigorous exercise most (5) days of the week.

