Data will be collected by study personnel including exercise physiologist, research fellow, head EKG technician and exercise student intern. The research team will assure that all data is collected. The data will be recorded in a de-identified manner using study IDs only. The key between participants and study IDs will be stored in a password protected electronic file. The data will be entered using a standard data management program (REDCap) on an ongoing basis. The data will be examined systematically for quality control and data cleaning purposes during the course of the study and again at the end. A portion of the data forms will be double entered for quality assurance purposes. The assistance of the Clinical Research Program will be solicited for technical support in these areas.

b. Quality Control Method The data will be examined systematically for quality control and data cleaning purposes quarterly during the course of the study and again at the study end prior to analysis.

c. Data Analysis Plan

The primary test of hypothesis is the comparison of change in Energy Expenditure (ΔEE) between baseline and final visit (12 weeks) in children receiving FITT Counseling plus BodyMedia as compared to children receiving physician counseling alone (standard of care/control). A two sample t-test will be used for this comparison. In the event of non-normality, the Wilcoxon rank sum test will be used. Secondary outcomes will be analyzed similarly. Linear regression will be used to adjust for any suspected confounding. In all tests, a two tailed p-value <0.05 will be considered statistically significant.

d. Study sample size and power considerations. . A total sample size of 40 (20/group) would provide adequate power to detect differences in physical activity counts as small as 0.9 standard deviations. Based on previous studies and clinical experience we expect $\leq 30\%$ attrition rate over 6 months: 30 patients per study group will be enrolled to ensure ≥ 20 per group complete the study

e. Study Organization

The study group will meet monthly to review progress and results of the study. Dr. [name] and [name] will review testing results as they are received. The Clinical Research Team will oversee recruitment and study activities for the Study.

f. Data and Safety Monitoring Plan

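### The primary test on change in energy expenditure does not pre-specify adjustment for baseline energy expenditure; it is valid, but gives up precision unless the slope on baseline is close to 1

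*Combined protocol and SAP*

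**What the plan says.** Section 5c (Data Analysis Plan) defines the primary comparison as the change in EE from baseline to 12 weeks, intervention against control, at two-sided 0.05. The test is unadjusted: "A two sample t-test will be used for this comparison". The fallback is also unadjusted: "In the event of non-normality, the Wilcoxon rank sum test will be used". For the other endpoints, "Secondary outcomes will be analyzed similarly". The only reference to adjustment is "Linear regression will be used to adjust for any suspected confounding". It names no covariate and is not the primary test.

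The baseline value will exist. Under Measures, the abstract has all patients "assessed at baseline and at the end of the study period directly for energy expenditure and physical activity using accelerometry". Section 4a (Study Design) adds that "patients who have worn the accelerometer for more than 8 hours per day for at least 3 days will be randomly assigned". Table 1 schedules accelerometry at baseline and at 12 weeks.

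Section 5d bases the sample size on 20 completers per group (30 enrolled) and claims adequate power to "detect differences in physical activity counts as small as 0.9 standard deviations". It gives no numerical power, no absolute SD and no correlation between visits.

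**The concern.** A change score already uses baseline EE, but it assumes that each unit of baseline carries over in full to week 12. If the true slope is well below 1, subtracting the whole baseline value adds noise that a fitted slope would remove. Regression to the mean and week-to-week variation in a one-week recording both push the slope in that direction.

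At stake is the width of the interval for the primary comparison in a trial that may finish with 20 patients per group and is powered only for a large difference. Validity is not at stake. Randomisation makes the unadjusted test unbiased, and chance imbalance at baseline is already reflected in its standard error. The confounding sentence would permit adjustment for baseline EE, but only as a choice left open until the data are seen.

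**Working it through.** **Inputs from the documents:** 20 per group completing, 30 enrolled, difference 0.9 SD, two-sided 0.05 (Sections 5c and 5d).

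**Assumptions:** 80% as the meaning of adequate power; 0.9 SD as the SD of the change in EE; the correlation ρ between baseline and week-12 EE; the SDs s0 (baseline) and s1 (week 12).

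**1. The plan's own figure.** n per group = 2 × (1.96 + 0.84)² / 0.9² = 19.4, rounded up to 20, which matches the plan. The normal approximation gives 81.2% power. The exact noncentral t (38 df, noncentrality 0.9 × √10 = 2.85) gives 79.2%, and 92.9% if all 30 per group complete. For attrition, 20 / 0.7 = 28.6, so 30 enrolled is sufficient.

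**2. Where the two analyses differ.** The slope is b = ρ × s1 / s0. Per-patient variance is:
- change score: s0² + s1² − 2ρ·s0·s1
- ANCOVA: s1² × (1 − ρ²)

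The difference is s0² × (1 − b)², which is never negative and is zero at b = 1. Estimating the slope costs a factor of about 1 + 1/(N − 4) = 1 + 1/36 = 1.028 and one degree of freedom (37 instead of 38).

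**3. Equal SDs, 20 per group.** The variance ratio becomes (1 + ρ)/2. At ρ = 0.5 it is 0.75, or 0.771 after the factor 1.028. The standardised effect is 0.9 / √0.771 = 1.025, the noncentrality is 1.025 × √10 = 3.24 on 37 df, and power is 88%. Interval widths come from simulation of bivariate normal data.

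| ρ | (1+ρ)/2 | × 1.028 | t-test power | ANCOVA power | Difference detectable at 80% (t-test: 0.91) | Median CI width, ANCOVA / t-test | Trials with wider ANCOVA interval |
|---|---|---|---|---|---|---|---|
| 0.3 | 0.65 | 0.668 | 79% | 92% | 0.74 | 0.82 | 1% |
| 0.5 | 0.75 | 0.771 | 79% | 88% | 0.80 | 0.89 | 4% |
| 0.7 | 0.85 | 0.874 | 79% | 84% | 0.85 | 0.94 | 15% |
| 0.8 | 0.90 | 0.925 | 79% | 82% | 0.875 | 0.97 | 27% |
| 0.9 | 0.95 | 0.976 | 79% | 80% | 0.90 | 1.00 | 48% |

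With 30 completers per group, the t-test has 93% and ANCOVA 99, 98, 96, 95 and 94%.

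**4. Unequal SDs, 20 per group, same five values of ρ.**
- s1 = 1.25 × s0 (slopes 0.375, 0.625, 0.875, 1.00, 1.125): ANCOVA 87, 82, 79, 78 and 80% against 79% for the t-test. Its interval is the wider one in 6, 25, 66, 80 and 48% of trials. The worst case is slope 1: about 1 point of power and a median interval 1.4% wider.
- s1 = 0.8 × s0: ANCOVA 97, 95, 93, 93 and 94%, a gain of 13 to 18 points.

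**5. If 0.9 is the SD of a single measurement** (20 per group, equal SDs): t-test against ANCOVA is 65 v 82% (ρ 0.3), 79 v 88% (0.5), 95 v 97% (0.7), and at least 99% for both (0.8).

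**6. Skewed data** (lognormal, log-SD 0.6 assumed, 20 per group): t-test 80%; Wilcoxon on the change 90, 91, 92, 92 and 92%; ordinary ANCOVA 91, 89, 86, 85 and 84%. The Wilcoxon test is therefore better than ANCOVA from ρ 0.5 upwards, and the fallback should stay.

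The complete rules were also compared, using Shapiro-Wilk p < 0.05 on the within-group-centred change as an illustrative trigger. On the lognormal data the plan's rule has 88, 89, 90, 90 and 90%. ANCOVA with the same Wilcoxon fallback has 93, 92, 92, 92 and 91%.

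**7. Type I error.** 4.8 to 5.2% for the t-test and for ANCOVA in every normal-data scenario; 4.8 to 5.7% for the plan's two-branch rule and 4.8 to 5.6% for the revised rule.

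**The case against.** The strongest reply is that nothing here is wrong. Both analyses are valid, the stated sample size reproduces, and the study is a pilot. The gain rests on a correlation, an SD ratio and a distribution that the documents do not give; over the scenarios run it goes from +18 points to −1. That stands, and it limits the point to efficiency. It also favours estimating the slope, because the planned test assumes a value for it.

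A second reply is that the protocol's preliminary studies report common non-compliance, with compliers and non-compliers moving apart. Variable response in the treated arm enlarges the residual variance and dilutes the gain. In an illustrative case, with extra treated-arm variation of 1 SD of the change, equal SDs otherwise and an effect of 0.9 pooled SD, the gain falls to about 8, 6, 3, 2 and 0 points at ρ 0.3 to 0.9. At ρ 0.9 the ANCOVA interval is the wider one in somewhat more than half of trials. The gain is smaller but not reversed.

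Third, regression is already planned, so only one covariate and its status are missing. That is true, and it is why the change is cheap. An unnamed covariate in a secondary model is still not a pre-specified primary analysis.

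**Conclusion.** The point holds as a recommended improvement. The primary analysis does not pre-specify baseline EE, although the value is available for every patient the t-test would include, since the change score needs it too. With 20 per group and equal SDs, adjustment raises power from 79% to between 80 and 92% for ρ from 0.9 down to 0.3, and the median interval is between 0 and 18% narrower. The gain vanishes as the slope approaches 1, where about 1 point of power may be lost.

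These sizes depend on the assumed correlation and SDs, and on reading 0.9 SD as the SD of the change in EE when Section 5d speaks of activity counts. The claim concerns the t-test branch only. It does not call the planned test biased or the sample size wrong.

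**What to change.** In Section 5c, make the primary analysis a linear regression of week-12 EE on randomised group with baseline EE as a pre-specified covariate, and report the adjusted difference with its 95% confidence interval. Using the change in EE as the response gives the same group estimate.

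- Keep the Wilcoxon test on the change for marked non-normality. Write down the criterion in advance, including whether it applies to the change or to the model residuals.
- Keep the t-test on the change as a sensitivity analysis. A rank-based ANCOVA may be added but is not needed.
- Analyse continuous secondary outcomes the same way where a baseline value exists. The condition is needed because Section 4a refers to "Lipid levels and blood pressures, when obtained for clinical visits in Preventive Cardiology Clinic", whereas Section 4e and Table 1 plan lipids and blood pressure for all participants.
- Label any other regression for suspected confounding as supportive.

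The cost is wording and one degree of freedom, with no new data, visits or patients. The worst result in the scenarios run was about 1 point of power and a median interval about 1% wider.

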1. We assessed the impact of an exercise prescription program upon the exercise capacity of adults with CHD. 18 patients aged 37 ± 13 years with a variety of CHD's underwent an initial cardiopulmonary exercise test (CPET) and were then provided with a prescription for a self-administered exercise program. Subjects were divided into "compliant" and "non-compliant" groups on the basis of their responses to questions administered at the time of the follow-up CPET. Peak VO_2 averaged 19.0 ± 7.1 ml/kg/min on the initial CPET and 19.4 ± 7.2 on the follow-up CPET ($p=NS$). Those that were "compliant" increased their peak VO_2 from 20.1 ± 9.3 to 21.5 ± 9.1 ml/kg/min ($p=0.025$). In contrast, the peak VO_2 of the non-compliant group decreased from 17.7 ± 3.2 to 17.1 ± 3.3 ml/kg/min ($p=NS$). Improvements in peak VO_2 of at least 1.0 ml/kg/min were observed in 7/9 compliant patients and in only 1/8 non-compliant patients ($p<0.02$). Compliant patients also achieved an average weight loss of 0.58 ± 3.8 kg, whereas non-compliant patients gained an average of 0.65 ± 1.8 kg. We concluded that when adults with CHD adhere to an exercise prescription, improvements in peak VO_2 are often achieved and successful weight loss is sometimes realized. However; poor compliance with exercise prescriptions was common, and limited the effectiveness of this therapeutic intervention.

2. We reviewed our clinical experience with FITT exercise prescription (Frequency, Intensity, Time, Type) and counseling combined with monthly motivational and educational follow-up contact in the form of mailings, e-mails, and phone calls affects physical activity as measured by self-report (METS). When available, we examined changes in physical fitness (VO_2 max), attitudes and self-efficacy regarding physical activity, BMI z-score, and cardiovascular risk factors.

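### The primary t-test on change can use only participants with a 12-week value, yet up to 30% loss is planned for and no handling of missing outcomes is stated; the result may be biased, in a direction the documents do not fix

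*Combined protocol and SAP*

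**What the plan says.** - **Primary test (5.c, Data Analysis Plan).** The arms are compared on change in EE between baseline and the 12-week visit: "A two sample t-test will be used for this comparison". The fallback is: "In the event of non-normality, the Wilcoxon rank sum test will be used". The threshold is: "a two tailed p-value <0.05 will be considered statistically significant".
- **Adjustment (5.c).** "Linear regression will be used to adjust for any suspected confounding". Baseline EE is not named as a covariate, and the sentence does not concern missing values.
- **Attrition (5.d).** At most 30% loss is expected, stated over 6 months. Thirty per arm are enrolled so that at least "20 per group complete the study".
- **Final measurement (4.a, Study Design).** All participants are asked to wear the armband for one week at the end. Before randomisation a minimum wear rule applies (more than 8 hours a day on at least 3 days). No such rule is given for the final week.
- **Burden by arm (4.a).** The intervention arm wears the device daily and uploads three times a week for 3 months. The control arm has no such task between the two measurement weeks.
- **Monitoring (5.f).** Drop-out is reviewed monthly.

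Neither 5.c nor any other section names an analysis population, a method for missing 12-week EE, or a sensitivity analysis.

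**The concern.** A change score exists only for someone with both measurements. Followed as written, the primary analysis is therefore an unadjusted complete-case comparison, although 5.c never calls it one. The sample size is built on the same completers.

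Randomisation protects the comparison of everyone randomised. It does not protect the comparison of those who remain if leaving is related to outcome and the relation, or the amount of loss, differs between arms. There is a concrete reason why it might differ here. The outcome is measured by wearing the same armband that one arm has been asked to wear and upload for 3 months, so people who tire of it may be the ones without a final week.

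At stake is whether a significant difference in EE change can be read as an effect of the programme. If population and imputation are chosen after the data are seen, the choice is open to challenge whichever way the result falls.

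**Working it through.** **1. The plan's own figure.** Inputs from 5.c and 5.d: 20 per arm, difference 0.9 SD, two-sided alpha 0.05. The power is only called adequate, so 80% is assumed.
- Normal formula: n = 2(1.96 + 0.84)²/0.9² = 19.4, so 20 per arm. Power at 20 per arm is 81.2% (normal) or 79.2% (noncentral t).
- Inflation: 20/(1 − 0.30) = 28.6, so 29 per arm against 30 enrolled; 30 × 0.70 = 21 expected completers per arm.

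The stated size reproduces. The allowance for attrition restores the number of observations and does nothing about which observations are lost.

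**2. Bias of a completers-only contrast.** In one arm let d be the share lost and g the mean change of stayers minus that of leavers, in SD units. The completer mean exceeds the full-arm mean by d × g. Hence

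bias = d_I × g_I − d_C × g_C (I = intervention, C = control; positive favours the intervention).

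The documents give neither d by arm nor g. The values below are assumptions: g from 0.5 to 0.9 SD, and d mostly at the planned ceiling of 30%. The false-positive rate comes from the noncentral t with the resulting completer numbers. With 21 per arm, the noncentrality is bias/√(2/21) = bias/0.309, on 40 degrees of freedom.

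| Assumed loss I / C | Selection | Bias (SD) | Two-sided error |
|---|---|---|---|
| 30% / 30% | equal in both arms | 0 | 5.0% |
| 30% / 30% | intervention only | 0.30 × 0.5 = +0.15 to 0.30 × 0.9 = +0.27 | 7.6% to 13.7% |
| 30% / 30% | control only | −0.15 to −0.27 | 7.6% to 13.7% |
| 30% / 10% | equal g | 0.20 × 0.5 = +0.10 to 0.20 × 0.9 = +0.18 | 6.3% to 9.3% |
| 10% / 30% | equal g | −0.10 to −0.18 | 6.3% to 9.3% |

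The largest value in the table, 0.27 SD, is 0.27/0.9 = 30% of the design effect. If loss were 15% per arm with selection in one arm only, the bias would halve to 0.15 × 0.5 = 0.075 to 0.15 × 0.9 = 0.135 SD, with error of about 6% to 8%.

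**3. What baseline adjustment gains.** With equal variances at the two times and correlation r between baseline and 12-week EE, the change score has variance 2σ²(1 − r) and the baseline-adjusted outcome has variance σ²(1 − r²). The ratio is (1 + r)/2. The documents do not give r. For assumed r of 0.3, 0.5 and 0.8 the ratio is 0.65, 0.75 and 0.90. The adjusted model also allows for loss that depends on baseline EE.

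**4. What a sensitivity analysis can and cannot do.** Take no true effect, 30% loss per arm and selection in the intervention arm only. Completers there sit at +0.15 to +0.27 SD. Giving leavers the control mean (0) leaves 0.70 × 0.15 = 0.105 to 0.70 × 0.27 = 0.189 SD. A shift equal to the true gap g would remove the bias, but g is unknown. Such an analysis shows how far the result depends on assumptions about the missing values. It does not remove bias from loss that depends on the unobserved outcome.

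**The case against.** **The direction is not shown, and this stands.** A reader might infer that the analysis is biased towards the intervention. The documents do not support that. The sign depends on between-arm differences in loss and selection, and no section gives loss by arm. Some features could hold intervention participants (weekly feedback, monthly phone follow-up). Others could hold controls (the FITT session promised after the study) or both arms (the completion gift certificate, and the wear requirement before randomisation).

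**The preliminary series do not settle it, and this stands too.** Section 3 reports that "poor compliance with exercise prescriptions was common, and limited the effectiveness of this therapeutic intervention" in adults with CHD, and that in an earlier clinic series "non-compliant patients either showed no change or worsened cardiovascular risk factors". It is tempting to read the contrast between compliers and non-compliers as the size of the bias here. But these are earlier series with no control arm described, so they cannot show differential loss. In the adult series compliance was classified at the follow-up exercise test, so the non-compliers were measured. Here, a non-complier who returns at 12 weeks stays in the t-test. Non-compliance is not dropout.

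**The 30% is a ceiling.** It is stated over 6 months, against 12 weeks of follow-up, so actual loss may be smaller. The error rates above illustrate assumptions and do not measure this trial's error.

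**The final week is already asked of everyone.** Section 4.a says so. It does not say whether this includes people who have stopped wearing or uploading the device.

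**Inflating enrolment for attrition is routine, and this is a pilot of 60.** Both are true, and neither answers the bias question. The plan does not expressly restrict the analysis to completers; its chosen tests have that effect.

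**Conclusion.** The point holds as a gap in the primary analysis. The stated tests use only participants with a 12-week value, up to 30% loss is provided for, and nothing is stated about missing outcomes. Bias is possible, with a plausible mechanism in the unequal device burden. Under the assumptions of 30% loss per arm and a leaver-stayer gap of 0.5 to 0.9 SD in one arm only, it is 0.15 to 0.27 SD towards the arm with the selection, and two-sided error rises from 5% to about 8% to 14%. It is zero if loss and selection match, and about half as large at 15% loss. The documents fix neither its size nor its sign. That uncertainty is itself the reason to specify the handling in advance. Separately, the unadjusted change score gives up precision that the baseline EE already collected would supply.

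**What to change.** In 5.c:
1. Compare participants in the arm to which they were randomised, using a linear model of 12-week EE with arm and baseline EE as terms, in place of the t-test on change.
2. State that the final armband week in 4.a is sought from every randomised participant, including those who stopped wearing or uploading the device, and define the wear that makes a final EE value valid.
3. Report loss by arm, with reasons.
4. Add a prespecified sensitivity analysis for missing 12-week EE, for example imputation from the control arm or imputation shifted by a range of deltas. Say that it probes, and does not remove, bias from loss that depends on the unobserved outcome.

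The cost is protocol wording, some effort to retrieve final weeks, and a little more analysis, with no added visits or participants. The estimate may be less favourable: if 30% of the intervention arm leave and gain nothing, a 0.9 SD effect among completers becomes 0.70 × 0.9 = 0.63 SD over all randomised.
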